## 11.5. Stopping Rules

Other than plans noted above, no stopping rules are planned for the study. The study may be prematurely discontinued by the Sponsor or Lead Investigator based on new safety information arising during the conduct of the study, in the case of AEs associated with the intervention, or for other reasons given by the Research Ethics Committee. The study may also be prematurely discontinued due to lack of recruitment or high attrition from the

study, as advised by the Study Steering Committee (SSC). If the study is prematurely discontinued, active participants will be informed and no further participant data will be collected. The Research Ethics Committee will be informed within 15 days of the early termination of the study. Participants may discontinue treatment at any time they choose or as recommended by study researchers (section 9.6).

# 12. Statistics

This protocol will be published to ensure transparency of study analyses and outcome reporting following the study.

## 12.1. Sample Size

As an initial feasibility study, a sample size calculation is not warranted. However, a sample of 40 participants permits estimation of a 50% dropout rate to within a 95% confidence interval of +/-15%.[Research Design Service. NIHR. Available at: https://www.rds-london.nihr.ac.uk/resources/justify-sample-size-for-a-feasibility-study/]. The existence of six repeated measures and focus on within-subjects change/variability will help boost power to observe effects without aiming to determine statistical significance of effects with any precision.

## 12.2. Analysis

Intention-to-treat analyses will be undertaken. In a few cases, a sensitivity analysis will be carried out, excluding non-adherent participants (these are specified below, where this applies).

Final analyses will be conducted after data collection has been completed and data cleaned. However, it is worth noting that an interim analysis is planned in May 2025 for all primary analyses below. This is for the purpose of initial pilot data to be included in funding applications being submitted for a feasibility study. No changes to the protocol or any procedures will be made based on this.

Variables will be summarised using descriptive statistics (i.e., mean and standard deviation [SD] or median and interquartile range [IQR] or frequencies and proportions, as appropriate).

Analyses pertaining to each outcome are listed below:

1. LiOR bioavailability as assessed by lithium levels in serum. This will be analysed descriptively, as above. Intraand inter- participant variation will be calculated. Overall changes over time may be assessed using a repeatedmeasures ANOVA (including only adherent participants taking a stable dose) to inform a potential future trial design.

2. LiOR acceptability as assessed by adherence rates (TRQ) and discontinuation. Rates of adherence (< 20% missed) will be assessed descriptively for each timepoint, and extent of adherence will also be described as a continuous (total TRQ score) measure. Rates of discontinuation (participant-report) will be described. Continuous adherence scores (for participants not discontinuing LiOR) over time will be tentatively compared using a repeated-measures ANOVA to inform a potential future trial design.

3. Subjective experiences of LiOR: negative experiences will be described via continuous LiSERS score measure, and positive experiences will be reported as participant-reported rates (yes/no to those listed). LiSERS scores over time (adherent participants only) will be compared using a repeated-measures ANOVA (possibly including dose as a between-subjects factor, pending dose variation within and between participants) to inform a potential future trial design.

4. Protocol feasibility as assessed by the rates (assessed descriptively) of attrition from the study, and of visits missed, and specific data for the putative primary outcomes i.e., mood measures.

There are three secondary outcomes, analysed as exploratory indications of change to inform a future definitive study design:

1. LiOR's biological effects, through assessment of key candidate blood-based biomarkers, namely neuroprotective growth factors (BDNF, VEGF) and inflammatory cytokines (IL-6, TNFa, IL-1b, IL-8, CRP) throughout the study. This will be examined using a repeated-measures ANOVA according to the intention-to-treat principle, with a sensitivity analysis to examine only adherent participants.

2. LiOr's effects on mood, through assessing changes in mood ratings (M3VAS, ISS, IDS, YMRS) throughout the study. These will be examined using a repeated-measures ANOVA according to the intention-to-treat principle, with a sensitivity analysis to examine only adherent participants.

3. LiOr's effects on cognition and psychosocial function, through assessing changes in THINC-IT and FAST scores respectively, throughout the study. These will be examined using a repeated-measures ANOVA according to the intention-to-treat principle, with a sensitivity analysis to examine only adherent participants.

Ancillary exploratory analyses will examine other wellbeing outcomes (e.g., EQ5D), service use, and a potential impact of bipolar features on outcomes during the study. Additional exploratory analyses using the data collected may be conducted.

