# 5. Background & Rationale

Lack of access to best-practice treatment is extremely common both in unipolar1 and bipolar2,3 affective disorders. Undertreatment is especially an issue for people experiencing depression with mixed features (DMF),4

where criteria for a depressive episode are met alongside concurrent symptoms of mania (e.g., activation, increased thought and speech rate).4 DMF is common5 and highly burdensome, not only with regard to a scant evidence base for effective treatments4 but also associations with bipolar disorder (progression to diagnosis or risk thereof)6, suicidality7 and psychosocial (including cognitive) disability.8 Moreover, DMF is under-detected in healthcare services and patients are routinely treated with standard antidepressant medications.4 These medications confer risk in DMF for worsening the manic symptom severity.4 Concomitant treatment with an antidepressant and a mood stabiliser could improve outcomes4,6, but this treatment strategy is rarely used in those without a full bipolar diagnosis.1,9

The gold standard mood stabiliser is lithium, usually prescribed in carbonate or citrate form.3 Despite its effectiveness against both symptoms of depression and (hypo)mania, including bipolar DMF,10 lithium is underused not least because the prescribed forms require regular blood monitoring to ensure patient safety.3 Thus, despite its putative effectiveness for people with DMF without a bipolar diagnosis, lithium is not routinely available for this population.

Our recent systematic review indicates effectiveness of lithium at 'sub-therapeutic' doses to patients with depression, mania and cognitive impairment (from 17 studies assessing intervention with lithium as low as 0.3mg elemental lithium.11 This is in contrast to 'therapeutic' doses, which average ~600-800mg lithium carbonate (containing >112mg ionic lithium).

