This is pertinent because these low doses are also evidenced to be safe, and a low-dose form of lithium (lithium orotate; LiOR) is available to purchase cheaply (without a prescription) as a supplement (up to 20mg ionic lithium) with our early work indicating that even lower doses (5 mg) result in detectable brain levels of lithium.12 If evidenced to be effective, LiOR could therefore be an accessible treatment option. My PPI work suggests it may also be desirable for patients, being a 'natural' substance. Despite evidence of safety11,12 LiOr has not been subject to clinical trials.11 This project seeks to determine whether commercially available LiOr has viability as an accessible adjunctive intervention for people with DMF.

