# 6. Study Objectives and Design

## 6.1. Study Objectives

This research aims to elucidate LiOr's plausibility, at a known safe dose, over an extended period in a preliminary study. This is a feasibility study comprising the preliminary work required prior to formal trials examining commercially available LiOr supplementation for DMF. No specific hypotheses are therefore proposed. In this open label study, people who constitute a target population for LiOR will be invited to take commercially available LiOr for up to six months to establish its plausibility as a putative intervention for trials. The specific objectives are to investigate up to six months of open-label 20mg daily LiOr to identify its within-subjects effects on the following as co-primary outcomes:

1. The potential to examine bioavailability of LiOr (i.e. whether lithium is present at detectable levels in the serum using a standard laboratory lithium test), assessing lithium levels in serum.

2. The acceptability of 20mg daily LiOr over 6 months (assessed by self-report adherence and discontinuation rates) to inform a future study design.

3. Description of any positive and/or negative experiences of 20mg daily LiOr over 6 months (assessed via participant-report) to inform a future study design.

4. The feasibility of the protocol including intervention delivery and assessment visits (including assessments mentioned above, plus putative primary (mood) and secondary (functioning, cognition) outcome measures and assessment of potential confounders). Overall feasibility will be assessed via missing data and study withdrawal rates.

An exploratory analysis of change will be undertaken as secondary objectives for measures over time to inform a future definitive study design:

1. LiOR's biological effects, through assessment of key candidate blood-based biomarkers, namely neuroprotective growth factors (BDNF, VEGF) and inflammatory cytokines (IL-6, TNFa, IL-1b, IL-8, CRP) between week 0 and week 26.

2. LiOr's effects on mood, through assessing changes in mood ratings between week 0 and week 26.

3. LiOr's effects on cognition and functioning, through assessing changes in cognitive and psychosocial function between week 0 and week 26.

These aims will be met via within-subjects comparisons for each timepoint relative to baseline (weeks 2, 4, 8, 16, 26).

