#### Screening session

Usually conducted over the phone by a trained researcher, or if potential participants are willing, by videocall (i.e., King's College London MS Teams) study information will be discussed and verbal consent for screening obtained. Verbal consent for screening will be recorded in a secure, password-protected spreadsheet for all potential participants. If the potential participant is willing, screening will provide an initial determination of eligibility. Specifically, eligibility will be assessed via screening procedures as follows:

- Open questions for self-report:
  - Eligible age range.
  - Willingness to try a commercially available lithium supplement.
  - Clinical health diagnoses (including bipolar disorder).
  - Severity of any diagnoses [participants are excluded if admitted to hospital within the past 6 months, have a planned admission in the upcoming 6 months, or attend outpatient/secondary services for an illness other than an affective disorder at least once per month].
  - Current treatments undergone for depression [name(s) of current medication, initiation / withdrawal and historical dose changes].
  - Ineligibility for lithium [as above; taking lithium, known cardiac disease or insufficiency, renal impairment, untreated thyroid dysfunction, breastfeeding, pregnancy, hyponatraemia, dehydration, regular use of NSAID, ACEI or diuretics, psoriasis, Addison's disease, Brugada syndrome or family history of Brugada.]
  - Ability to travel to one of the research sites on a regular basis over 6 months.
- MINI interview, MDD module, to establish current depressive episode and suicide module to establish nonsignificant suicide risk.
- (if not completed within Qualtrics within the last week), Internal States Scale [ISS] to establish presence of mixed features within current depressive episode.
- Ability to communicate fluently in English: researcher-defined, via ability to communicate during discussions about understanding of participant information and prior questions.
- Ability to provide informed consent to participate: researcher-defined, via communications and understanding of the procedures being consented to.

If inclusion criteria are met following this, the W0 assessment will be scheduled.

All assessments are expected to take place in the morning, as (post-LiOR initiation), blood samples are taken in the morning, at least 12 hours after the last LiOR dose, to avoid acute effects of lithium intake.

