#### W0: Baseline Assessment

Before the assessment begins, written informed consent will be completed by the participant. The following measures will then be administered.

Blood test

• 2 x tube serum for the detection of lithium levels, using a standardized validated assay, with a lower limit of detection of 0.1mmol/L and candidate inflammatory markers and growth factor proteins.

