## 11. Assessment of Safety

#### 11.1. Assessment of Therapy Safety

Safety is not an outcome of this study, as the supplement has been evidenced to be safe (having been available and used without supervision, in the community, for decades). However, the welfare of our participants is paramount, and we will closely monitor information obtained from participants to ensure their safety. Specifically, this includes monitoring of lithium levels and wellbeing measures (as soon as each information are available to the research team). Monitoring and proposed actions comprise:

- a. If any abnormalities are noted from clinical blood tests, participants and their GPs will be informed within one working day by study researchers. NB these are likely to be incidental, not associated with the intervention, given evidence to date of safety.
- b. If any lithium levels exceed 0.6mmol/L, the dosing regime will be lowered from 20mg to 10mg as maximum dose as soon as practicable. This would be highly unexpected, given that the typical dose of lithium carbonate required to achieve therapeutic levels (0.6-0.8mmol/L) is 600-800 (approximately 6-8 times the elemental equivalent in LiOR 20mg).
- c. If >50% participants (at any point in time) report a desire to reduce from 20mg, the dosing regimen will be lowered from 20mg to 10mg as soon as practicable.
- d. If any wellbeing concerns arise in general, participants will be contacted within one working day by a study researcher for a wellbeing discussion and to provide support (i.e., study-related actions, signposting e.g., to support or healthcare services).

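### Serum lithium on 20 mg is likely to lie close to the assay's detection limit, yet section 12.2 commits to variation in levels and not to the detectable proportion that section 6.1 sets as co-primary 1

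*Protocol*

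**What the plan says.** Section 6.1 defines the first co-primary objective as "whether lithium is present at detectable levels in the serum using a standard laboratory lithium test". Section 12.2 analyses it thus: "LiOR bioavailability as assessed by lithium levels in serum. This will be analysed descriptively, as above". The words 'as above' point to a general sentence that offers mean and SD, median and IQR, or frequencies and proportions, whichever suits. Section 12.2 then states firmly that variation within and between participants will be calculated, and adds an option: "Overall changes over time may be assessed using a repeatedmeasures ANOVA", limited to adherent participants on a stable dose.

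The blood test entry under the W0 assessment describes the assay "with a lower limit of detection of 0.1mmol/L". The screening section times post-initiation samples in the morning, "at least 12 hours after the last LiOR dose", with no upper bound. Section 11.1(b) argues that high levels would be surprising because "the typical dose of lithium carbonate required to achieve therapeutic levels (0.6-0.8mmol/L) is 600-800 (approximately 6-8 times the elemental equivalent in LiOR 20mg". The synopsis lets participants move down from 20 mg to 15, 10 or 5 mg.

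**The concern.** Section 11.1 uses its dose ratio to show that levels will be far below the therapeutic range. The same ratio also says how far below, and the answer is close to the lowest level the assay can detect. The protocol does not carry this through to section 12.2.

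Two things follow. First, where many results can only be reported as below 0.1, a mean, an SD and a split of variance within and between participants depend on the number put in their place. Second, the natural summary for a yes/no objective is a proportion, and item 1 of section 12.2 does not name one. Items 2 and 3 of the same section do name rates where they are wanted, for adherence and for positive experiences.

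Co-primary 1 is meant to inform the design of a later trial, and section 12.2 plans an interim analysis of all primary outcomes in May 2025 to supply pilot data for funding applications. A mean and SD that depend on a coding choice would be poor input to either.

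**Working it through.** **Inputs from the protocol**

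- Therapeutic level 0.6-0.8 mmol/L at 600-800 mg carbonate, put at 6-8 times the elemental lithium in 20 mg of the supplement (section 11.1).
- Therapeutic doses "which average ~600-800mg lithium carbonate (containing >112mg ionic lithium" (section 5).
- The supplement sold "as a supplement (up to 20mg ionic lithium" (section 5).
- Detection limit 0.1 mmol/L (W0 blood test).
- N = 40 (section 12.1).

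**Assumptions not in the protocol**

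- Serum level is proportional to elemental dose, for orotate as for carbonate.
- The therapeutic range refers to a similar sampling time after the dose.
- Levels are lognormal, with a coefficient of variation (CV) between 20% and 50%. The protocol gives no SD, so this range is illustrative.

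**Step 1: reproduce the stated ratio.** The lithium fraction of Li₂CO₃ is 2×6.94 / (2×6.94 + 12.011 + 3×15.999) = 13.88/73.89 = 0.188. So 600 mg holds 112.7 mg and 800 mg holds 150.3 mg of lithium. Divided by 20 mg, these give 5.6 and 7.5, in line with the stated 6-8. The section 5 figure gives 112/20 = 5.6. The ratio is sound.

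**Step 2: expected level on 20 mg** = therapeutic level / ratio.

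- Matching ends of the ranges: 0.6/6 = 0.8/8 = 0.10 mmol/L.
- Exact elemental masses: 0.6×20/112.7 = 0.8×20/150.3 = 0.106 mmol/L.
- Crossed ends: 0.6/8 = 0.075 and 0.8/6 = 0.133 mmol/L; with exact masses, 0.080 and 0.142 mmol/L.

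**Step 3: lower permitted doses** = 20 mg level × dose/20.

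| Dose | From 0.10 | From 0.075 to 0.133 |
|---|---|---|
| 15 mg | 0.075 | 0.056 to 0.100 |
| 10 mg | 0.050 | 0.038 to 0.067 |
| 5 mg | 0.025 | 0.019 to 0.033 |

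Only the top of the 15 mg range reaches the limit (0.142×0.75 = 0.106 with exact masses).

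**Step 4: share of 20 mg results below 0.1** = Φ(ln(0.1/median)/s), with s = √ln(1+CV²).

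| Median (mmol/L) | Share below 0.1, CV 20% to 50% |
|---|---|
| 0.075 | 93% to 73% |
| 0.100 | 50% at any CV |
| 0.107 | 37% to 44% |
| 0.133 | 7% to 27% |

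At the extreme crossed value of 0.142 the share would be 4% to 23%.

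**Step 5: effect of coding.** Take a median of 0.10 and a CV of 30%, so that the true mean is 0.104 and the true SD 0.031.

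| Non-detects set to | Mean | SD |
|---|---|---|
| 0 | 0.064 | 0.067 |
| 0.05 | 0.089 | 0.043 |
| 0.1 | 0.114 | 0.023 |

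The SD ratio is 0.067/0.023 = 2.9 from the coding rule alone.

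**Step 6: precision of a detectable proportion.** At 50% detectable and N = 40, 1.96×√(0.25/40) = 0.155, the same ±15 points that section 12.1 quotes for dropout. An exact (Clopper-Pearson) interval for 20/40 is 33.8% to 66.2%, or about ±16 points. With 20 evaluable participants the normal approximation gives ±21.9 points.

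**The case against.** A reader might infer that the planned analyses fail and that detectability will go unreported. The protocol does not support that. Its menu of descriptive summaries includes frequencies and proportions, so a detectable proportion is permitted and could be counted from data already collected. The ANOVA is optional and excludes non-adherent participants and those whose dose changes. A median tolerates some censoring. Many non-detects would in themselves go some way to answering the question in section 6.1.

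Nor does the protocol state an expected level on the supplement. The 0.10 figure is scaled from a rough safety argument, and it assumes that orotate behaves like carbonate, which is close to what co-primary 1 explores. At the favourable end few results would be lost. It would also be too strong to say that the laboratory suppresses readings under 0.1, since only a detection limit is given.

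Another tempting reading is that W0, where almost all values should be non-detects because current lithium users are excluded, enters the lithium ANOVA. Section 6.1 speaks generally of comparisons with baseline, but section 12.2 does not list W0 for this outcome, and its adherence and stable-dose filter suggests on-treatment visits.

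Finally, a rule for values below the limit may sit in a statistical analysis plan that is not shown, so its absence is not a finding.

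All of this stands, and it limits the point. Two things remain. Variation in levels is a firm commitment, and it is the quantity most sensitive to coding. And the summary that answers the stated objective is left as one option among several.

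**Conclusion.** The concern holds in a limited form. Under dose proportionality and comparable sampling times, the protocol's own ratio places the expected 20 mg level at about 0.10 mmol/L (0.075 to 0.14), around the detection limit, with the lower doses mostly under it. A substantial share of non-detects is likely but poorly determined: about 40-50% centrally, and roughly 7% to 93% for medians of 0.075 to 0.133 and CVs of 20-50%. At the central estimate the committed variation summary could change about threefold with coding. The detectable proportion is allowed but not promised.

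This is a mismatch between an objective and its stated analysis, worth correcting but below must-fix, because the count of detectable results can still be recovered later. The time between dose and draw cannot be recovered reliably, which is the reason to act before visits take place. Confidence is moderate, since the expected level is inferred.

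**What to change.** In section 12.2, name as the main summary for co-primary 1 the proportion of participants with serum lithium at or above 0.1 mmol/L at each on-treatment visit, by current dose, with an exact 95% confidence interval.

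Report continuous levels, variance components and any ANOVA from on-treatment visits only. Use numeric readings below the limit if the laboratory can release them; otherwise use a method for left-censored data.

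Record the clock times of the last capsule and of the blood draw at each visit, so that differences in sampling time can be described.

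The cost is a few sentences in section 12.2, two extra fields on the case report form, a question to the laboratory, and a coarser headline than a mean level. No dose, visit or sample needs to change.

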Endpoints:	Week 0: Baseline assessment, pre-intervention	
	Week 2, 4, 8, 16: Intermediary follow-up assessments Week 26: Final follow-up assessment	
Sample Size:	40 individuals.	

Summary Of Eligibility Criteria:	Aged between 18-65 at study entry. Meet DSM-5 criteria for a current depressive episode and exceed thresholds indicating presence of mixed features. Undergoing antidepressant treatment (stable intervention/dose unchanged for >6 weeks). No diagnosis of bipolar disorder received. No other severely impairing health condition. No contraindications to lithium treatment (including currently taking lithium). No significant suicidality.		
Intervention (Description, frequency, details of delivery):	Open label lithium orotate supplement as available commercially, 20mg once per day. Participants will be instructed to begin taking the supplement the day after the baseline assessment for a period of up to six months. If participants prefer to move to a lower dose, they can titrate down to 15mg, 10mg or 5mg. Intervention is self-managed, but participants are provided with information about the supplement and have access to the research team to answer any questions or provide further information. Participants who discontinue will remain in the study, although will not be required to attend intermediary follow- up visits, which collect information related to the intervention. We will ask them to attend the final endpoint visit, however.		
Comparator Intervention:	n/a		
Maximum Duration Of Treatment Of A Participant:	6 months / 26 weeks (i.e., from baseline up until the final follow-up assessment). Participants are permitted to discontinue the supplement at any time they wish.		
Version And Date Of Final Protocol:	[to be completed]		
Version And Date Of Protocol Amendments:	n/a as yet		

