## 7. Study Intervention

#### 7.1. Therapy/Intervention Details

This section relates to the lithium orotate (LiOR) supplementation (N=40). The study will not interfere with usual care in any way, although the study team will inform participants' named healthcare professionals (GPs or secondary care clinician if under outpatient care) of their participation which includes LiOR supplementation. LiOr is available in 5mg, 10mg or 20mg doses. As our previous research has shown that individuals frequently take 20mg LiOR once per day of their own accord, without need for titration, we encourage participants to start from this dose. We do not permit a higher dose, as there is no evidence to date of commercial LiOR supplementation at these doses. We will permit a lower dose, if participants desire: as capsules are 5mg each, participants can select to take fewer capsules daily and we will collect this information. We will measure the rates and duration of doses taken. We will support participants if they have questions. Participants will receive bottles/pots as can be purchased, which contain 60 x 5mg capsules (which covers up to 20mg per day for 15 days). Between weeks 0 -2, and 2 – 4, one supply can be provided at the earlier time until the upcoming visit. Subsequently, or if visits are not conducted within 15 days (i.e., participants would otherwise have depleted supply), the next supply of LiOR will be delivered via special delivery Royal Mail with receipt confirmed. This will be undertaken on the basis of checking with participants regularly the quantity of LiOR they have remaining to ensure a continual supply. At the 26-week assessment, participants will be asked to return any remaining LiOR. The lithium orotate purchased is manufactured by Swanson www.swanson.co.uk. [name] team at Newcastle University have examined the quantity and consistency (both within and between batches) determining these to be accurate and stable. Swanson have provided King's Clinical Trial Unit with quality documents (including demonstration of quality, purity and potency at the point of release of the product onto the market, and over-time). These were reviewed by the CTU's pharmacist who has confirmed appropriateness for progressing in the study with these. The supplement will be purchased directly from the supplier and stored in locked cupboards, in a locked office at King's College London, that only the research team will have access to. These will be a cool, dry place as per manufacturer instructions and we will ensure that the product expiry date outlives the date to participants' next supply date. Records will be kept of distribution to participants as per above. The products will not be unsealed or altered in any way before distribution to participants.

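### Co-primary 2 is worded as acceptability of 20 mg daily, but neither of its measures refers to dose, and the adherence denominator is not stated

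*Protocol*

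**What the plan says.** Objective 2 in Protocol 6.1, repeated in the Synopsis, is "The acceptability of 20mg daily LiOr over 6 months (assessed by self-report adherence and discontinuation rates) to inform a future study design". The Synopsis also allows dose changes: "If participants prefer to move to a lower dose, they can titrate down to 15mg, 10mg or 5mg". Section 7.1 confirms that participants may take fewer 5 mg capsules a day and adds "We will measure the rates and duration of doses taken".

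In 12.2, item 2 is introduced as "LiOR acceptability as assessed by adherence rates (TRQ) and discontinuation" and has these parts:

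- A binary rate: "Rates of adherence (< 20% missed) will be assessed descriptively for each timepoint". Section 7.3 gives the matching 80% threshold on the Tablets Routine Questionnaire (TRQ). Neither place sets a dose condition, and 12.2 gives no denominator.
- The total TRQ score, described as a continuous measure.
- The participant-reported discontinuation rate, described separately.
- A tentative repeated-measures ANOVA of "Continuous adherence scores (for participants not discontinuing LiOR) over time".

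According to the Synopsis, participants who discontinue stay in the study and are asked to attend the final visit, but need not attend the intermediary ones. Section 11.1 contains two regimen-level reductions to 10 mg: item b, on serum lithium, and item c, which begins "If >50% participants (at any point in time) report a desire to reduce from 20mg".

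**The concern.** The objective names a dose and the measures do not. A participant who drops to one capsule a day in week 3 and rarely misses it meets the adherence definition and has not discontinued. On both measures that person looks the same as someone who kept 20 mg for six months.

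The gap is specific to this item. In 12.2, item 1 limits its ANOVA to participants on a stable dose and item 3 may include dose as a factor. Item 2, the one whose objective is acceptability of a stated dose, makes no use of the dose data promised in 7.1.

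The missing denominator adds to this. The TRQ is completed at W2, W4, W8, W16 and W26, so someone who has stopped may contribute no TRQ at the remaining intermediary visits. A rate computed from available questionnaires would then describe continuers.

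The stake is the next study. The outcome is meant to inform its design, and 12.2 schedules an interim run of all primary analyses in May 2025 to supply pilot data for funding applications. A dose and an expected exposure could be taken from a figure that refers neither to 20 mg nor to everyone who started.

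**Working it through.** **The plan's own figure.** Section 12.1 says that 40 participants estimate a 50% dropout rate to within ±15%. The Wald half-width is 1.96 × √(0.5 × 0.5 / 40) = 0.155, and the Wilson half-width is 0.148. The exact (Clopper-Pearson) interval is 33.8% to 66.2%. The stated figure reproduces to rounding and is not disputed. It presumes all 40 in the denominator, which item 2 does not state for adherence.

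**Which measures respond to which behaviour (12.2 item 2 as written).**

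| Participant | <20% missed? | Discontinued? | Kept 20 mg? |
|---|---|---|---|
| Takes 20 mg regularly to W26 | yes | no | yes |
| Moves to 5 mg, takes it regularly to W26 | yes | no | no |
| Stops | TRQ may be absent until W26 | yes | no |

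The first two rows are the same on both planned measures. Stopping is picked up by the discontinuation rate; stepping down is picked up by neither.

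**Illustration of size.** The documents give no rates of stopping, reducing or adherence, so everything here is assumed. Let 40 start, 10 stop, 10 reduce and 20 stay on 20 mg, with 90% adherence among those still taking capsules.

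- Adherent at any dose, continuers only: 0.9 × 30 = 27; 27/30 = 90%.
- Adherent at any dose, all starters: 27/40 = 67.5%.
- Adherent and on 20 mg, all starters: 0.9 × 20 = 18; 18/40 = 45%. Exact 95% CI 29.3% to 61.5%.

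With stopping and reducing both expressed as shares of all starters, the last proportion is (1 − stop − reduce) × 0.9. It runs from 0.8 × 0.9 = 72% (10% stop, 10% reduce) to 0.1 × 0.9 = 9% (50% stop, 40% reduce). The continuer rate stays at 90% throughout because it is fixed by assumption.

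**Second set of assumptions, separating the two effects.** Adherence among continuers is about 80%, and counts are rounded to whole people.

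| Stop | Reduce | Continuers, any dose | All 40, any dose | All 40, at 20 mg |
|---|---|---|---|---|
| 0 | 0 | 32/40 = 80% | 32/40 = 80% | 32/40 = 80% |
| 0 | 20 | 32/40 = 80% | 32/40 = 80% | 16/40 = 40% |
| 10 | 0 | 24/30 = 80% | 24/40 = 60% | 24/40 = 60% |
| 10 | 8 | 24/30 = 80% | 24/40 = 60% | 18/40 = 45% |
| 20 | 10 | 16/20 = 80% | 16/40 = 40% | 8/40 = 20% |

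Row 2 is the pure dose effect: nobody stops, so choosing the right denominator does not remove it. Row 3 is the pure denominator effect: with all 40 in the denominator it disappears. Row 1 shows that the gap is zero if nobody reduces or stops.

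**The case against.** Three stronger readings are tempting, and the protocol does not support them.

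- A reader might infer that the plan counts people who step down as successes. It sets no success criterion, 6.1 disclaims specific hypotheses, and item 2 is mainly descriptive. The definition is silent on dose; that is not a rule to count reducers as having accepted 20 mg.
- A reader might infer that discontinuers are dropped from the adherence results. The text excludes them only from the tentative ANOVA. The per-visit rates and the described total score carry no such restriction, 12.2 opens with an intention-to-treat statement, and discontinuation is reported as a separate part of the same outcome. Stopping is therefore not hidden. Discontinuers are also asked to attend W26, where the TRQ is given.
- A reader might infer that acceptability will be overstated. That depends on how many reduce or stop, which nobody yet knows, and on whether dose summaries are reported beside this outcome.

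Two further points are fair. Item c of 11.1 is a safety-monitoring action, so it is not evidence that the protocol treats wanting a lower dose as non-acceptance. And 7.1 does commit to measuring doses taken, so the data should exist.

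What remains is the mismatch. The measures are fixed inside the objective and again in 12.2, so this is not a detail left to an analysis plan. The intention-to-treat sentence does not say how an absent TRQ is counted, and no sentence links the dose data to item 2.

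**Conclusion.** The point holds as a mismatch between objective and measure. Followed as written, co-primary 2 cannot register a participant who did not keep 20 mg, and its adherence rates have no stated denominator. Reported adherence can overstate acceptability of 20 mg; the documents do not show that it will. Under the assumed rates, 90% adherence among continuers sits beside 45% of all starters adherent at 20 mg. Other assumptions take the gap from zero to much larger. The figures show direction and possible scale and are not a forecast. The change is worth making because it alters what one of the four co-primary outcomes can conclude.

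**What to change.** In 12.2 item 2, using the dose data planned in 7.1:

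- Report, at each post-baseline visit including W26, the proportion of all participants given LiOr who are still taking 20 mg with at least 80% adherence, with an exact 95% CI. State that all participants given LiOr form the denominator.
- Beside it, tabulate dose status at each visit: on 20 mg, reduced by preference, reduced under 11.1b or 11.1c, stopped, lost. Keeping the 11.1 reductions separate prevents a protocol-driven change from being read as participant preference.
- Label TRQ scores and the ANOVA among continuers as describing continuers.

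Alternatively, reword objective 2 in 6.1 and the Synopsis as acceptability of flexible dosing up to 20 mg, and still state the denominator. Neither route changes any dosing rule.

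Time-to-reduction curves and a capsule-count check on the TRQ are optional. For the latter, 7.1 plans stock checks and return of leftover capsules but does not say that remaining counts are recorded.

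The cost is wording in 6.1, the Synopsis and 12.2, slightly more tabulation, and possibly a less favourable headline figure.
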